5.3 Exclusion criteria

Patients eligible for this study must not meet any of the following criteria:

1. Gastrointestinal condition which could impair absorption of study medication;
2. Congenital long QT syndrome, or any known history of torsade de pointes (TdP), or family history of unexplained sudden death;
3. Clinically uncontrolled hypertension (after standard antihypertensive treatment, systolic blood pressure ≥ 140 mmHg and/or diastolic blood pressure ≥ 90 mmHg);
4. Undergone a bone marrow or solid organ transplant;
5. Any toxicities from prior treatment that have not recovered to \leq CTCAE Grade 1 before the start of study drug, with the exception of hair loss or fatigue;
6. Patients who have previously participated in clinical trials of ERK inhibitors drug;
7. Allergic to similar drugs or their excipients;
8. HIV(human immunodeficiency virus) infection, active hepatitis B or hepatitis C patients (HBsAg positive patients also detected HBV/hepatitis B virus) DNA $\geq 10^3$ copies or ≥ 200 IU/ml; HCV (hepatitis C virus) antibody test results are positive, and HCV RNA PCR test results are positive);
9. Uncontrolled or severe intercurrent medical condition:
 - Unstable angina pectoris ≤ 3 months prior to starting study drug;
 - Acute myocardial infarction ≤ 3 months prior to starting study drug;
10. Symptomatic CNS metastases that are neurologically unstable or requiring increasing doses of steroids to control CNS disease. Note: Controlled CNS metastases are allowed. Radiotherapy or surgery for CNS metastases must have been completed >2 weeks prior to study entry. No new neurologic deficits on clinical examination and no new findings on CNS imaging are permitted. Steroid use for management of CNS metastases must be at a stable dose for two weeks preceding study entry;
11. Any cancer-directed therapy (chemotherapy, radiotherapy, hormonal therapy, biologic or immunotherapy, Chinese medicine/Chinese patent medicine with anti-tumor effect,etc.) within 28 days or 5 half-lives, whichever is shorter;

12. Major surgery within 4 weeks prior to first dose;
13. Any use of an investigational drug within 28 days or 5 half-lives (whichever is shorter) prior to the first dose of HH2710;
14. Pregnant or breast-feeding women;
15. Severe chronic or active infections requiring systemic antibacterial, antifungal or antiviral therapy, including tuberculosis infection, etc
 - Severe infections within 4 weeks prior to the first dose, including but not limited to hospitalization for complications of infection, bacteremia, or severe pneumonia.
 - Received therapeutic oral or IV antibiotics within 2 weeks prior to the first dose of study drug
16. Any important medical illness or abnormal laboratory finding that would increase the risk of participating in this study;
17. A history or current evidence/risk of retinal vein occlusion, central serous retinopathy or choroidneovascularization (CNV).
18. Concurrent therapy with any other investigational agent;
19. Concomitant malignancies or previous malignancies with less than 2 years disease-free interval at the time of enrollment; (But basal cell carcinoma skin cancer, cervical CIS(carcinoma in situ), CIS of the breast, localized or low Gleason grade prostate cancer, and < T2 bladder cancer can be included);
20. Current treatment with agents including vitamins, supplements, and herbal supplements that are metabolized solely through CYP3A4(See [Appendix 14.7](#));
21. Severe chronic obstructive pulmonary disease, severe asthma, pneumoconiosis, asbestosis and other occupational lung diseases.
22. A history of acute or chronic pancreatitis, surgery of the pancreas, or any risk factors that may increase the risk of pancreatitis;
23. Contraception (See [Appendix 4](#) Women of child-bearing age and contraceptive measures):

Patients who do not meet the following conditions will be excluded,

 - For women: Negative pregnancy test for females of child-bearing potential; must be surgically sterile, postmenopausal (defined as no menstrual cycle for at least 12 consecutive months), or compliant with an acceptable contraceptive regimen (2 highly effective forms, such as oral contraceptives, condom with spermicide, etc.) during and for 6 months after the treatment period. Abstinence is not considered an adequate contraceptive regimen;

- For men: Must be surgically sterile, or compliant with a contraceptive regimen (as above) during and for a minimum of 6 months after the treatment period.

6 Treatment

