	
not limited to hospitalization for complications of infection, bacteremia, or severe pneumonia.
 
 - Received therapeutic oral or IV antibiotics within 2 weeks prior to the first dose of study drug. 
16. Any important or severe medical illness or abnormal laboratory finding that would increase the risk of participating in this study;
 
17. A history or current evidence/risk of retinal vein occlusion, central serous retinopathy or choroidneovascularization (CNV) ;
 
18. Concurrent therapy with any other investigational agent;
 
19. Concomitant malignancies or previous malignancies with less than 2 years disease-free interval at the time of enrollment; (But basal cell carcinoma skin cancer, cervical CIS(carcinoma in situ), CIS of the breast, localized or low Gleason grade prostate cancer, and < T2 bladder cancer can be included)
 
20. Current treatment with agents including vitamins, supplements, and herbal supplements that are metabolized solely through CYP3A4 (see Appendix 14.7);
 
21. Severe chronic obstructive pulmonary disease, severe asthma, pneumoconiosis, asbestosis and other occupational lung diseases.
 
22. A history of acute or chronic pancreatitis, surgery of the pancreas, or any risk factors that may increase the risk of pancreatitis;
 
23. Contraception (See Appendix 4 Women of child-bearing age and contraceptive measures):
 
Patients who do not meet the following conditions will be excluded,
 
 - For women: Negative pregnancy test for females of child-bearing potential; must be surgically sterile, postmenopausal (defined as no menstrual cycle for at least 12 consecutive months), or compliant with an acceptable contraceptive regimen (2 highly effective forms, such as oral contraceptives, condom with spermicide, etc.) during and for 6 months after the treatment period. Abstinence is not considered an adequate contraceptive regimen; - For men: Must be surgically sterile, or compliant with a contraceptive regimen (as above) during and for a minimum of 6 months after the treatment period.
Investigational and reference therapy	HH2710
Efficacy assessments	Tumor assessment per RECIST v1.1

[figure not shown]
Safety assessments	Incidence, type and severity of Adverse Events (AEs), physical examination findings, clinical laboratory values, vital signs and Electrocardiograms (ECGs).

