1.2.1.1 Preclinical experience

1.2.1.1.1 Preclinical drug metabolism and pharmacokinetics

Pharmacokinetic studies conducted in Sprague-Dawley rats and Beagle dogs suggest that HH2710 has an acceptable pharmacokinetic behavior. After intragastric administration, HH2710 is absorbed fast with a $t_{1/2}$ of 1.68~3.60 hrs (rat) and 1.40~2.54 hrs (dog), respectively. Within the dosage range of 10 to 40 mg/kg (rats, fasting) and 3 to 12 mg (dogs, fasting), the exposure of HH2710 is greater than dose proportional following intragastric gavage, and the bioavailability

was 46.9 – 86.5% (rat) and 47.8 – 72.6% (dog) in these two species. After intragastric administration of 10 to 40 mg/kg HH2710 to rats, the mean HH2710 C_{max} values were 2.95 to 10.6 $\mu\text{g}/\text{mL}$, and the mean HH2710 AUC_{0-t} values were 13.1 to 96.4 $\mu\text{g}\cdot\text{h}/\text{mL}$, respectively. After single intragastric administration of 3 to 12 mg/kg HH2710 to dogs, the mean HH2710 C_{max} values were 0.74 to 3.50 $\mu\text{g}/\text{mL}$, and the mean HH2710 AUC_{0-t} values were 3.44 to 20.9 $\mu\text{g}\cdot\text{h}/\text{mL}$, respectively. After the rats were given intragastric administration of HH2710, it was mainly distributed in the adrenal gland, liver, gastrointestinal tract, kidney and pancreas. The apparent volume of distribution at steady state (V_{ss}/F) of rats and dogs was 0.562 and 1.14 L/kg, respectively. HH2710 did not easily pass blood brain barrier and hardly entered blood cells. The value of apparent total plasma clearance was low with the value of 5.93 (rat) and 7.29 (dog) $\text{mL}/\text{min}/\text{kg}$. There is no sex difference in exposure and no obvious accumulation over consecutive daily administration for a week. Elimination is by metabolism (CYP3A) then excretion mainly in feces. Monooxidated metabolite HH3529 is the major metabolite of HH2710 produced through CYP3A.

The major metabolite HH3529: After a multiple intragastric administration of 10, 20 and 40 mg/kg HH2710 to rats, the exposures of HH3529 were approximately 57-121% of those of HH2710, increased proportionately with dose. Plasma concentrations of HH3529 peaked at 2-4 hours post-dose. After a multiple intragastric administration of 3, 6 and 12 mg/kg HH2710 to dogs, the exposures of HH3529 were only approximately 3% of those of HH2710.

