6.4 Concomitant medications

6.4.1 Permitted concomitant therapy

The patient must be told to notify the investigational site about any new medications he/she takes after the start of the study drug. All medications (other than study drug) and significant non-drug therapies (including physical therapy, herbal/natural medications and blood transfusions) administered during the study must be listed on the Concomitant Medications or the Procedures and Significant Non-Drug Therapies CRF.

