6.4.2 Permitted concomitant therapy requiring caution and/or action

HH2710 inhibits CYP2C8, CYP2C9, CYP2C19, CYP3A4/5 (midazolam, as substrate) and CYP3A4/5 (testosterone, as substrate) *in vitro* with IC₅₀s of 4.37 μ M, 4.52 μ M, 8.75 μ M, 8.38 μ M, and 7.03 μ M. The drug-drug interaction potential of HH2710 due to inhibition of CYP2C8, CYP2C9, CYP2C19 and CYP3A4/5 is low based on its clinical exposure. Caution should be taken

when substrates of CYP2C8, CYP2C9, CYP2C19 and CYP3A4/5 are combined with HH2710, in particular those with a narrow therapeutic margin.

HH2710 induces CYP2B6 and CYP3A4 at 10 μ M *in vitro*. The drug-drug interaction potential of HH2710 due to induction of CYP2B6 and CYP3A4 is low based on its clinical exposure. Caution should be taken when sensitive substrates of CYP2B6 and CYP3A4 are combined with HH2710.

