6.4.3 Prohibited concomitant therapy

Anticancer therapy (chemotherapy, biologic or radiation therapy, surgery or Chinese medicine/Chinese patent medicine with anti-tumor effect) other than the study treatments must not be given to patients while the patient is on the study. If such agents are required for a patient, then the patient must be discontinued from the study.

In vitro data indicate Drug HH2710 is metabolized primarily by CYP3A, therefore strong inhibitors of CYP3A4 (e.g., clarithromycin, itraconazole, ketoconazole, telithromycin, etc.) and strong CYP3A4 inducers (e.g., carbamazepine, rifampicin, St. John's wort, etc.) should be avoided. Gastric acid reducing agents and sensitive substrates of CYP2C8, CYP2C9, and CYP2C19 also should be avoided. Refer to [**Appendix 14.7**](#) for a list of prohibited medications. This list may not be comprehensive.

Current treatment with agents including vitamins, supplements, and herbal supplements that are metabolized solely through CYP3A4 should be prohibited.

In vitro data indicate HH2710 is a potential P-gp substrate. Strong P-gp inhibitor will likely increase the exposure level of HH2710. Strong P-gp inhibitor should be avoided (Refer to [**Appendix 14.8**](#)).

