14.7 Appendix 7 CYP3A4 inhibitor and inducer

CYP3A4 inhibitor	CYP3A4 inducer
Potent:	
 - Anticonvulsants, mood stabilizer - Carbamazepine - Phenytoin (anticonvulsants) - Oxcarbazepine - Barbiturate - Phenobarbital Modafinil - Butalbital Nafcillin - Bosentan Nevirapine - Enzalutamide Primidone - Etravirine Rifabutin - Fosphenytoin Semagacestat - Mephennytoin Talviraline - Methylphenobarbital Thioridazine - Mitotane Vemurafenib - St John's wort (hypericum perforatum) - Bactericide - Rifampicin - Rifabutin - Non-nucleoside reverse transcriptase inhibitor - Efavirenz - Nevirapine - Hypoglycemic agents - Pioglitazone - Troglitazone - Glucocorticoid (glucose increased, immunosuppression) - Modafinil (stimulant)
Intermediate:	
Weak:	

 - Fluoxetine/norfluoxetine - Cimetidine (H₂-antagonist) 	

CYP3A4 inhibitor	CYP3A4 inducer
- Buprenorphine (analgesic) - Cafestol (unfiltered coffee) - Orphenadrine	

Sensitive Substrates of CYP2C8, CYP2C9, and CYP2C19

CYP2C8	CYP2C9	CYP2C19
Repaglinide	Tolbutamide, warfarin	Lansoprazole, omeprazole

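### Exclusion criterion 20 screens out CYP3A4 substrates but cites the inhibitor/inducer appendix, and no entry criterion or washout covers, as a class, the strong CYP3A4 and P-gp modulators that Section 6.4.3 says to avoid

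*Protocol*

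**What the plan says.** Criterion 20 in Protocol Section 5.3 reads "Current treatment with agents including vitamins, supplements, and herbal supplements that are metabolized solely through CYP3A4(See", the reference being to Appendix 14.7. The protocol summary has the same rule and citation: "herbal supplements that are metabolized solely through CYP3A4 (see Appendix 14.7". The appendix is headed "14.7 Appendix 7 CYP3A4 inhibitor and inducer". Its only substrate list covers CYP2C8, CYP2C9 and CYP2C19.

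On the drug's own clearance, Section 1.2.1.1.1 (rat and dog data) says "Elimination is by metabolism (CYP3A) then excretion mainly in feces". Section 6.4.3, citing in vitro data, says "HH2710 is metabolized primarily by CYP3A, therefore strong inhibitors of CYP3A4" should be avoided, and says the same of strong CYP3A4 inducers. On transport it says "Strong P-gp inhibitor will likely increase the exposure level of HH2710", and it refers to Appendix 14.8 for drugs to avoid. Section 6.4.3 states no start time and no interval before the first dose.

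On the opposite direction, HH2710 acting on other drugs, Section 6.4.2 says "The drug-drug interaction potential of HH2710 due to inhibition of CYP2C8, CYP2C9, CYP2C19 and CYP3A4/5 is low based on its clinical exposure".

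The protocol does set pre-dose intervals for other drugs: the shorter of 28 days and 5 half-lives for cancer-directed therapy (criterion 11) and investigational drugs (criterion 13), and 2 weeks for therapeutic antibiotics (criterion 15).

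**The concern.** Criterion 20 is the only one of the 35 entry criteria (12 inclusion, 23 exclusion) that names a CYP enzyme, and none names P-gp. It addresses drugs that HH2710 might affect, an interaction the protocol rates as low. It does not address drugs that change HH2710 exposure, the interaction behind the inhibitor, inducer and P-gp rules in Section 6.4.3. A site that turns to the cited appendix to apply criterion 20 finds the wrong kind of list.

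The 21-day DLT window and the single-dose PK profile both begin on C1D1. Inhibition persisting from a recently stopped drug raises early exposure, and persisting induction lowers it. With cohorts of 3, Table 6-5 escalates only if no patient has a DLT, so one patient whose exposure does not match the nominal dose can affect the decision.

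**Working it through.** **Entry rules set against Section 6.4.3**

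| Drugs to avoid under 6.4.3 | Entry rule for the class | Pre-C1D1 interval for the class | Partial cover |
|---|---|---|---|
| Strong CYP3A4 inhibitors | None | None | Criterion 15: antibiotics within 2 weeks (clarithromycin, telithromycin), and severe or active infection needing systemic antifungals or antivirals. Criterion 8: HIV and active hepatitis B or C, hence most users of the listed antivirals |
| Strong CYP3A4 inducers | None | None | Criterion 15: rifampicin. Criterion 11: anticancer agents such as vemurafenib. Criterion 8: antiretrovirals such as efavirenz. Criterion 20: arguably St. John's wort, as a herbal supplement listed in the cited appendix |
| Strong P-gp inhibitors | None | None | Criterion 15: clarithromycin. Criterion 8: ritonavir combinations. Criterion 11: lapatinib |

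Drugs left with no interval include carbamazepine (named in 6.4.3), phenytoin (Appendix 14.7), verapamil (Appendix 14.8), and azoles used for mild infection or prophylaxis. Use among eligible patients is plausible: criterion 3 admits treated, controlled hypertension and criterion 10 admits controlled CNS metastases. The table relies on headings and legible entries, not on apparent gaps in the extracted Appendix 14.7 lists.

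**Size of carry-over from an inhibitor**

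Inputs:
- DLT window T = 21 days (Section 2.3).
- Example dose 300 mg QD (Table 6-4).
- Exposure taken as proportional to dose, because Section 2.3 reports no apparent dose-dependence of PK.
- Assumed, not in the documents: fraction of clearance blocked at first dose, f = 0.50 to 0.625.
- Assumed, not in the documents: offset half-life h = 1 to 3 days.

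With k = ln 2 / h, the exposure ratio on day t is 1 / (1 − f·e^(−kt)). Its mean over T days is ln[(e^(kT) − f) / (1 − f)] / (kT).

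Lowest case, f = 0.50, h = 1: kT = 14.556, and the mean is (14.556 + 0.693) / 14.556 = 1.048. Then 300 × 1.048 = 314 mg.

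Highest case, f = 0.625, h = 3: kT = 4.852 and e^(kT) = 128, so the mean is ln(127.375 / 0.375) / 4.852 = 5.828 / 4.852 = 1.201. Then 300 × 1.201 = 360 mg.

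| f | h (days) | Mean ratio, first 24 h | Mean ratio, 21 days | 300 mg acts like | Ratio at C1D15 |
|---|---|---|---|---|---|
| 0.50 | 1 | 1.58 | 1.05 | 314 mg | 1.00 |
| 0.50 | 2 | 1.74 | 1.10 | 329 mg | 1.00 |
| 0.50 | 3 | 1.81 | 1.14 | 343 mg | 1.02 |
| 0.625 | 1 | 1.87 | 1.07 | 320 mg | 1.00 |
| 0.625 | 2 | 2.15 | 1.13 | 340 mg | 1.00 |
| 0.625 | 3 | 2.28 | 1.20 | 360 mg | 1.03 |

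The first-24-hour column uses the same formula with T = 1. Under these assumptions the C1D1 profile is distorted materially, average exposure over the DLT window modestly, and C1D15 PK hardly at all. Slower offset would raise every column. Residual induction acts in the opposite direction and is not quantified here.

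**The case against.** **Section 6.4.3 already controls these drugs.** It restricts them on study, inclusion 12 requires compliance with trial requirements, and concomitant medication is recorded from screening. That limits the gap to entry and washout but does not close it: none of these provisions sets an interval, and screening has a maximum of 28 days but no minimum.

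**Section 6.4.1 might seem to delay the control.** It speaks of "any new medications he/she takes after the start of the study drug", and a reader might infer that Section 6.4.3 applies only from first dose. The documents do not support this. The sentence concerns patients notifying the site, and Section 6.4.3 gives no start time. The gap exists on either reading.

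**The stronger reading of size does not hold.** A reader might treat full inhibition as lasting all of Cycle 1. Then AUC would rise 1 / (1 − 0.50) = 2.0-fold or 1 / (1 − 0.625) = 2.67-fold, making 300 mg QD act like 600 or 800 mg QD, the doses of the suspended expansion and escalation cohorts. With an assumed DLT rate of 0.15, the probability of escalating from 3 patients would fall from 0.85³ = 0.614 to 0.85² × 0.55 = 0.397 if one over-exposed patient had rate 0.45. That scenario is continued co-administration, which Section 6.4.3 already addresses. The gap concerns a drug that has been stopped.

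**Misattribution would not pass unseen.** Escalation patients have dense PK on C1D1 and C1D15, and Sections 6.2.3.1 and 6.2.4 bring available PK into dose decisions. This is real mitigation, but partial: it depends on someone linking an outlying profile to a stopped drug, and it acts after the patient has been exposed.

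**The inputs are thin.** The CYP3A evidence is in vitro and animal, P-gp involvement is described as potential, and the human CYP3A share and the number of patients affected are not given. This is accepted; the size above is conditional on stated assumptions.

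**The program has stopped**, as SAP Section 7 states. A new criterion cannot help patients already treated.

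**Conclusion.** The point stands at moderate size. Criterion 20 is aimed at one class of drug and cites a list of another. No entry criterion or washout covers, as classes, the modulators that the protocol itself says to avoid, so full compliance still allows carry-over into C1D1. With f = 0.50 to 0.625 and an offset half-life of 1 to 3 days, both assumed, the 21-day mean AUC ratio is about 1.05 to 1.20, equivalent to about 315 to 360 mg for a 300 mg QD patient. The effect on C1D1 is larger, and slower offset would increase both.

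A reader might infer from the Appendix 14.7 citation that criterion 20 was meant to exclude inhibitors and inducers. That is possible, but its wording does not say so. Nor do the documents show that any enrolled patient was affected or that the observed DLT came from an interaction. The change is worth making for any further enrolment or reuse of the protocol. For data already collected, the medication summaries in SAP Section 8.5 give a starting point for identifying recent users when DLT and PK results are interpreted.

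**What to change.** Add to Section 5.3 and to the protocol summary: *Use of a strong CYP3A4 inhibitor, strong CYP3A4 inducer or strong P-gp inhibitor (Appendix 14.8) within 14 days or 5 half-lives before C1D1, whichever is longer.*

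Restrict the CYP3A4 part to the agents in Appendix 14.7 that are strong, and mark them there. The inducer list includes glucocorticoids, so citing it whole could exclude the stable-dose steroid patients whom criterion 10 admits. Correct criterion 20's citation as well, by giving it a CYP3A4 substrate list or removing the reference.

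The 14 days is a proposal, not a figure the protocol gives for these drugs; it matches the antibiotic interval in criterion 15. Under the assumptions above, 14 days brings the exposure ratio at first dose to at most 1 / (1 − 0.625 × 2^(−14/3)) = 1.03.

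The cost is one criterion in two places and one citation. No new data are needed, because concomitant medication is already recorded at screening. Most affected patients would wait about 2 weeks, within the 28-day screening window. A few would wait longer or be excluded because the drug has a long half-life or cannot be stopped.

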6.1 Study treatment

A treatment cycle is defined as 21 days for the purposes of scheduling procedures and evaluations.

The investigational product in the study is shown as below:

- Active ingredient: HH2710;
- Strength: 25 mg capsule, 100 mg capsule;
- Excipients: include but not limit to Lactose, Silicified Microcrystalline Cellulose, Talc, Colloidal silicon Dioxide, Crospovidone, and Magnesium Stearate;
- Storage temperature: 10-30°C , protected from light.

6.1.1 Dosing regimen

The dosing and treatment schedule, as shown in the below.

Table 6-1 Proposed Dose and treatment schedule of Phase I

Bayesian optimal interval (BOIN) design incorporated with an accelerated titration Schedule of HH2710				
Dose Level	Dose of HH2710	Patient	Pharmaceutical form and route of administration	Frequency and/or Regimen
Level 1	25mg	3	Capsules for oral use	QD at C1D1, then BID from C1D2 (21 days/cycle)
Level 2	50mg	3	Capsules for oral use	BID (21 days/cycle)
Level 3	100mg	3+N [#]	Capsules for oral use	BID (21 days/cycle)
Level 4	300mg	3+N [#]	Capsules for oral use	QD (21 days/cycle)
Level 5	400mg (Total daily dose*)	3+N	Capsules for oral use	QD/BID (21 days/cycle)
Level 6	600mg (Total daily dose*)	3+N	Capsules for oral use	QD/BID (21 days/cycle)

Level 7	800mg (Total daily dose*)	3+N	Capsules for oral use	QD/BID (21 days/cycle)
#: The number of pts enrolled in each dose is specified by the BOPIN rules;				
*: Proposed daily dose is the total dose each day with QD or BID dose frequency.				
Dosing frequency and dose level may be adjusted on the basis of available pharmacokinetic data and safety.				

Table 6-2 Dose and treatment schedule of Phase II

Dose extension Schedule of HH2710			
Dose Level	Dose of HH2710	Pharmaceutical form and route of administration	Frequency and/or Regimen
1	RP2D	Capsules for oral use	QD or BID (21 days/cycle)

In Phase I, the first 3 patients will be administered orally (in the fasted state) HH2710 capsule once daily (QD) at the first day, then sampling for PK, from the second day, HH2710 capsule will be administered orally on a continuous twice daily (BID) schedule, on a flat scale of mg/day and not individually adjusted by weight or body surface area. The fourth and later patients will be administered with HH2710 capsule twice daily (BID) from the first day of cycle 1, patients will be instructed to take their study medication 12±2 hour interval. Based on human PK data, from the fourth dose level, the patients will be administered with HH2710 capsule once daily (QD). The Investigator must instruct the patient to take the study drug exactly as prescribed.

- Except on days of single dose PK sampling, patients should take HH2710 capsule follow the doctor's advice at approximately the same time each day starting at Cycle 1 Day 1, Patient should not eat until 2 hours after HH2710 administration.
- Each dose of HH2710 is to be taken with a glass of water (at least 8 ounces—approximately 250 mL) and consumed over as short a time as possible (i.e., Not slower than 1 capsule every 2 minutes).
- Patients should be instructed to swallow the capsules whole and not to chew them.
- Patients will be instructed to take their study medication follow the doctor's advice. The study medication should be taken with at least 8 ounces water at the same time each day in the fasted state (2 hours before food or 2 hours after food). If a dose is not taken within 2 hours of the planned dosing time, the missed dose should not be replaced.
- On days when PK blood samples are to be collected, patients will be instructed to hold their dose until arrival at the study site. HH2710 will be administered at the site in the morning. The exact time of drug administration should be recorded in the appropriate eCRF (Electronic Case Report/Record Form). The PK blood draws will be supervised by a member of the

research team. If a patient vomits within 4 hours of HH2710 dosing, the time and severity of vomiting should be recorded on the eCRF.

- Patient who is observed to vomit an intact capsule after dosing in the clinic during the PK measurements may receive a substitute dose of drug. However, patients should be instructed NOT to take a substitute capsule if vomiting occurs after self-dosing at home. Missed doses should be skipped and not taken as a double dose at the next dosing time point.
- All dosages prescribed and dispensed to the patient and all dose changes during the study must be recorded on the source document and/or drug account record eCRF page.

